6.1.3 Data Quality Assurance

The research team will monitor each patient's dataset throughout the study. Source document review will be made against entries on the eCRF and a quality assurance check will be performed to ensure that the investigator is complying with the protocol and regulations. In addition, after the research team (data managers) completes the CRFs a research nurse or physician at the NCI will review and verify the data.

6.2 DATA SHARING PLANS

6.2.1 Human Data Sharing Plan

What data will be shared?

I will share human data generated in this research for future research as follows:

- Coded, linked data in an NIH-funded or approved public repository.
- Coded, linked data in BTRIS (automatic for activities in the Clinical Center)

How and where will the data be shared?

Data will be shared through:

- An NIH-funded or approved public repository. Clinicaltrials.gov.
- BTRIS
- Publication and/or public presentations.

When will the data be shared?

- Before publication.
- At the time of publication or shortly thereafter.

6.2.2 Genomic Data Sharing Plan

Unlinked genomic data will be deposited in public genomic databases such as dbGaP in compliance with the NIH Genomic Data Sharing Policy.

6.3 RESPONSE CRITERIA

For the purposes of this study, patients should be re-evaluated for response every 12 weeks.

Response and progression will be evaluated in this study using the international criteria proposed by the revised Response Evaluation Criteria in Solid Tumors (RECIST) guideline (version 1.1). Changes in the largest diameter (unidimensional measurement) of the tumor lesions and the shortest diameter in the case of malignant lymph nodes are used in the RECIST criteria.

6.3.1 Definitions

Evaluable for toxicity: All patients will be evaluable for toxicity from the time of their first treatment with sunitinib or everolimus.

Evaluable for objective response: Only those patients who according to RECIST guideline (version 1.1) have measurable disease present at baseline, have been started on therapy with everolimus or sunitinib, and have had their disease re-evaluated will be considered evaluable for response. These patients will have their response classified according to the definitions stated below. (Note: Patients who exhibit objective disease progression prior to the end of cycle 1 will also be considered evaluable.)

Evaluable Non-Target Disease Response: Patients who have lesions present at baseline that are evaluable but do not meet the definitions of measurable disease, have been started on therapy with everolimus or sunitinib, and have had their disease re-evaluated will be considered evaluable for non-target disease. The response assessment is based on the presence, absence, or unequivocal progression of the lesions.

6.3.2 Disease Parameters

Measurable disease: Measurable lesions are defined as those that can be accurately measured in at least one dimension (longest diameter to be recorded) as:

- By chest x-ray: ≥ 20 mm;
- By CT scan:
 - Scan slice thickness 5 mm or under as ≥ 10 mm with CT scan
 - Scan slice thickness > 5 mm: double the slice thickness
- With calipers on clinical exam: ≥ 10 mm.

All tumor measurements must be recorded in millimeters (or decimal fractions of centimeters).

Metastatic lymph nodes. To be considered pathologically enlarged and measurable, a lymph node must be ≥ 15 mm in short axis when assessed by CT scan (CT scan slice thickness recommended to be no greater than 5 mm). At baseline and in follow-up, only the short axis will be measured and followed.

Non-measurable disease. All other lesions (or sites of disease), including small lesions (longest diameter < 10 mm or pathological lymph nodes with ≥ 10 to < 15 mm short axis), are considered

non-measurable disease. Bone lesions, leptomeningeal disease, ascites, pleural/pericardial effusions, lymphangitis cutis/pulmonitis, inflammatory breast disease, and abdominal masses (not followed by CT or MRI), are considered as non-measurable.

Note: Cystic lesions that meet the criteria for radiographically defined simple cysts should not be considered as malignant lesions (neither measurable nor non-measurable) since they are, by definition, simple cysts.

‘Cystic lesions’ thought to represent cystic metastases can be considered as measurable lesions, if they meet the definition of measurability described above. However, if non-cystic lesions are present in the same patient, these are preferred for selection as target lesions.

Target lesions. All measurable lesions up to a maximum of 2 lesions per organ and 5 lesions in total, representative of all involved organs, should be identified as target lesions and recorded and measured at baseline. Target lesions should be selected on the basis of their size (lesions with the longest diameter), be representative of all involved organs, but in addition should be those that lend themselves to reproducible repeated measurements. It may be the case that, on occasion, the largest lesion does not lend itself to reproducible measurement in which circumstance the next largest lesion which can be measured reproducibly should be selected. A sum of the diameters (longest for non-nodal lesions, short axis for nodal lesions) for all target lesions will be calculated and reported as the baseline sum diameters. If lymph nodes are to be included in the sum, then only the short axis is added into the sum. The baseline sum diameters will be used as reference to further characterize any objective tumor regression in the measurable dimension of the disease.

Non-target lesions. All other lesions (or sites of disease) including any measurable lesions over and above the 5 target lesions should be identified as non-target lesions and should also be recorded at baseline. Measurements of these lesions are not required, but the presence, absence, or in rare cases unequivocal progression of each should be noted throughout follow-up.

6.3.3 Methods for Evaluation of Measurable Disease

All measurements will be taken and recorded in metric notation using a ruler or calipers. All baseline evaluations will be performed as closely as possible to the beginning of treatment and never more than 4 weeks before the beginning of the treatment.

The same method of assessment and the same technique will be used to characterize each identified and reported lesion at baseline and during follow-up.

Conventional CT: This guideline has defined measurability of lesions on CT scan based on the assumption that CT slice thickness is 5 mm or less. If CT scans have slice thickness greater than 5 mm, the minimum size for a measurable lesion should be twice the slice thickness. Ideally, the same type of scanner should be used and the image acquisition protocol should be followed as closely as possible to prior scans. Body scans should be performed with breath-hold scanning techniques, if possible.

Tumor markers: Chromogranin A levels, which represents a constitutive neuroendocrine secretory protein, is the most widely accepted biomarker. Chromogranin A was compared to a panel of biomarkers and proved to be the most accurate, with a specificity of 85.7% and sensitivity of 67.9%[\[101\]](#). Chromogranin A is elevated in 60- 80% of patients with neuroendocrine tumors. The National Cancer Institute (NCI) recommends that serial

measurements of CgA be incorporated into prospective clinical trials[49]. Chromogranin A level will be checked within 2 weeks prior to treatment, and every 3 months after treatment initiation.

68-Gallium DOTATATE: We and others have demonstrated that 68-Gallium DOTATATE is more sensitive for detecting sites of metastatic disease than anatomic imaging studies [102]. Therefore, we will also use 68-Gallium DOTATATE imaging results that show new lesions within 18 months follow up time to define progression of disease. All patients must have a target lesion as identified by conventional CT or MRI, however, to be eligible for enrollment in the study to evaluate response by RECIST criteria.

6.3.4 Response Criteria

6.3.4.1 Evaluation of Target Lesions

Complete Response (CR): Disappearance of all target lesions. Any pathological lymph nodes (whether target or non-target) must have reduction in short axis to <10 mm.

Partial Response (PR): At least a 30% decrease in the sum of the diameters of target lesions, taking as reference the baseline sum of diameters.

Progressive Disease (PD): At least a 20% increase in the sum of the diameters of target lesions, taking as reference the smallest sum on study (this includes the baseline sum if that is the smallest on study). In addition to the relative increase of 20%, the sum must also demonstrate an absolute increase of at least 5 mm. (Note: the appearance of one or more new lesions is also considered progressions).

Stable Disease (SD): Neither sufficient shrinkage to qualify for PR nor sufficient increase to qualify for PD, taking as reference the smallest sum of diameters while on study.

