3.5 CRITERIA FOR REMOVAL FROM PROTOCOL THERAPY AND OFF STUDY CRITERIA

3.5.1 Criteria for removal from protocol therapy

The criteria that take the subject off active protocol therapy include:

- Progressive disease on each study arm
- Participant requests to be withdrawn from active therapy
- Unacceptable Toxicity as defined in Section **3.3**
- Investigator discretion
- Positive pregnancy test

In all cases, a safety follow up visit will be conducted within approximately 30 days of the last dose of study drug therapy.

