6.3.4.3 Evaluation of Best Overall Response

The best overall response is the best response recorded from the start of the treatment until disease progression/recurrence (taking as reference for progressive disease the smallest measurements recorded since the treatment started). The patient's best response assignment will depend on the achievement of both measurement and confirmation criteria.

For Patients with Measurable Disease (i.e., Target Disease)

Target Lesions	Non-Target Lesions	New Lesions	Overall Response	Best Overall Response when Confirmation is Required*
CR	CR	No	CR	≥4 wks. Confirmation**
CR	Non-CR/Non-PD	No	PR	≥4 wks. Confirmation**
CR	Not evaluated	No	PR	
PR	Non-CR/Non-PD/not evaluated	No	PR	
SD	Non-CR/Non-PD/not evaluated	No	SD	Documented at least once ≥4 wks. from baseline**
PD	Any	Yes or No	PD	no prior SD, PR or CR
Any	PD***	Yes or No	PD	
Any	Any	Yes	PD	

* See RECIST 1.1 manuscript for further details on what is evidence of a new lesion.
 
** Only for non-randomized trials with response as primary endpoint.
 
*** In exceptional circumstances, unequivocal progression in non-target lesions may be accepted as disease progression.
 
Note: Patients with a global deterioration of health status requiring discontinuation of treatment without objective evidence of disease progression at that time should be reported as “symptomatic deterioration.” Every effort should be made to document the objective progression even after discontinuation of treatment.
				

For Patients with Non-Measurable Disease (i.e., Non-Target Disease)

Non-Target Lesions	New Lesions	Overall Response
CR	No	CR
Non-CR/non-PD	No	Non-CR/non-PD*
Not all evaluated	No	not evaluated
Unequivocal PD	Yes or No	PD
Any	Yes	PD

* ‘Non-CR/non-PD’ is preferred over ‘stable disease’ for non-target disease since SD is increasingly used as an endpoint for assessment of efficacy in some trials so to assign this category when no lesions can be measured is not advised
		

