6.3.5 Duration of Response

Duration of overall response: The duration of overall response is measured from the time measurement criteria are met for CR or PR (whichever is first recorded) until the first date that recurrent or progressive disease is objectively documented (taking as reference for progressive disease the smallest measurements recorded since the treatment started).

The duration of overall CR is measured from the time measurement criteria are first met for CR until the first date that progressive disease is objectively documented.

Duration of stable disease: Stable disease is measured from the start of the treatment until the criteria for progression are met, taking as reference the smallest measurements recorded since the treatment started, including the baseline measurements.

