6.3.6 Progression-Free Survival

PFS is defined as the duration of time from start of each treatment to time of progression or death, whichever occurs first.

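### The plan does not say consistently whether the reference for progression restarts at cross-over; read literally, a patient who is only stable on the second drug can be progressed at its first scan

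*Combined protocol and SAP*

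**What the plan says.** All references are to the combined protocol and SAP.

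- **Progression rule (6.3.4.1).** Target-lesion progression is "At least a 20% increase in the sum of the diameters of target lesions". The comparison point for that rise is fixed by the words "taking as reference the smallest sum on study (this includes the baseline sum if that is the smallest on study". There is an absolute condition too: "the sum must also demonstrate an absolute increase of at least 5 mm". A note adds that "the appearance of one or more new lesions is also considered progressions". Stable disease is also defined against the smallest sum while on study.
- **Best overall response (6.3.4.3).** The reference is worded differently: "taking as reference for progressive disease the smallest measurements recorded since the treatment started".
- **Duration of response (6.3.5).** Again "taking as reference the smallest measurements recorded since the treatment started".
- **PFS (6.3.6).** Time runs "from start of each treatment to time of progression or death".
- **Cross-over (3.1.1).** Patients move to the other drug after progression or unacceptable toxicity, within 3 months of stopping the first. A CT or MRI is required within 4 weeks beforehand, but it is listed as part of confirming eligibility. It is not called a new baseline.
- **Leaving therapy and leaving study (3.5.1, 3.5.2).** "Progressive disease on each study arm" ends protocol therapy. Progression is not among the off-study criteria, so a patient who crosses over is still on study.

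**The concern.** The plan has a two-drug sequence, but its progression rule is written for one continuous period on study. A patient who crosses over because target lesions grew starts the second drug already at or above the progression threshold measured from the first-drug nadir. If that nadir remains the reference, a second drug that holds the tumour steady is scored as a failure at its first assessment, due at 12 weeks under Section 6.3. If the reference restarts with the drug, the same scan is stable disease.

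The choice decides second-drug PFS, which Section 6.3.6 defines by starting a clock with each treatment. It also decides second-drug stable disease, which matters because Section 1.1.2 counts stable disease in the overall response rate. Section 6.3.7 leaves independent review of responses to the end of the study, so sites and reviewers could apply different references to the same images. Section 3.5.1 ties the same call to the end of protocol therapy.

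**Working it through.** **1. The plan's own figure, to see whether it is touched.** Section 8 states 80% power per arm with 44 patients, median PFS 18 against 11 months, one-sided alpha 0.10, by the Brookmeyer-Crowley method. Assume exponential PFS and ignore censoring before month 11. Then S(11) under the alternative is 0.5^(11/18) = 0.655, and its standard error is sqrt(0.655 × 0.345 / 44) = 0.072. Power is Φ[(0.655 − 0.5)/0.072 − 1.282] = 81.0%, or 79.1% when the critical value uses the null variance. The stated 80% is reproduced. It concerns first-line PFS only, so no second-drug rule enters it.

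**2. Progression threshold in Section 6.3.4.1.** Let N be the smallest sum on study. Progression begins at

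T = max(1.2N, N + 5 mm).

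The 5 mm condition governs when N is below 25 mm; otherwise T = 1.2N.

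**3. The two readings on one patient.** Take N = 100 mm and a cross-over sum of 120 mm.

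| Reading | Reference | Progression from |
|---|---|---|
| 6.3.4.1 as written | first-drug nadir, 100 mm | 1.2 × 100 = 120 mm |
| Cross-over scan as baseline, no shrinkage | 120 mm | 1.2 × 120 = 144 mm |

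Any second-drug sum from 120 mm to just under 144 mm is progression under the first reading and not under the second. An unchanged sum of 120 mm falls in that band; 119 mm is not progression under either.

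If the sum first falls to 110 mm on the second drug, the second threshold becomes 1.2 × 110 = 132 mm, and the band narrows to 120–132 mm. The readings coincide only once the sum is back at the old nadir, a fall of 1 − 100/120 = 16.7%.

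**4. Shrinkage needed to leave progression under the literal rule.** For N of at least 25 mm and a cross-over sum of N(1 + g), the sum must fall by just over 1 − 1.2/(1 + g).

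| Growth above nadir at cross-over, g | Shrinkage needed |
|---|---|
| 20% | just above 0 |
| 25% | 4.0% |
| 30% | 7.7% |
| 40% | 14.3% |
| 44% | 16.7% |
| 50% | 20.0% |

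The documents give no distribution of g; 20% to 50% is an assumed range. For smaller tumours the 5 mm condition applies. With N = 15 mm, T = 20 mm, and a cross-over sum 50% above nadir (22.5 mm) needs a fall of 1 − 20/22.5 = 11.1%.

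**5. Cross-over for toxicity.** These patients need not have progressed, but the literal rule can reach them. As an illustration, a sum falls from 100 to 70 mm on the first drug and regrows to 85 mm around the change of drug, where a gap of up to 3 months is allowed. The rise is 85/70 − 1 = 21% and 15 mm, which is progression under Section 6.3.4.1 although 85 mm is below the original baseline.

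**The case against.** The strongest reply is that the plan, read as a whole, already implies a per-drug reference. Section 6.3.4.3 sets the progression reference from the start of treatment, Section 6.3.5 does the same, and Section 6.3.6 speaks of each treatment. Section 6.3.3 wants baseline imaging no more than 4 weeks before treatment, and Section 3.1.1 asks for a scan in just that window before cross-over. This has force, and it is why the defect is an inconsistency and not a settled wrong rule. It does not remove the defect. In a two-drug sequence, treatment in the singular can mean either drug or the whole course, while the operative definitions of progressive and stable disease both say on study.

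A second reply is that little depends on it. Second-drug PFS is not a named objective in Section 1.1, Section 8 specifies no analysis of it, and response is described there as descriptive. That limits the weight of the point. Even so, Section 6.3.6 defines PFS for each treatment, Section 8 bases response on all patients receiving treatment, and no rule says how second-drug scans are to be read.

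A reader might infer three stronger things, none of which the documents support:

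- **That tumours must shrink about 17% to avoid progression.** That is the fall from 1.2 times nadir back to nadir. Avoiding progression needs only a sum below the threshold.
- **That most crossed-over patients would show about 3 months of second-drug PFS by construction.** The sunitinib response rates in Table 2 (9% and 2.4%) do not show this. Partial response in this plan needs a 30% decrease, so they do not count smaller falls, and the share crossing over for toxicity is unknown.
- **That a patient with a new lesion can never avoid progression on the second drug.** The trigger is the appearance of a lesion, and one already on the pre-cross-over scan has arguably not appeared during the second drug. The text is unclear here, not decisive.

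**Conclusion.** The point holds as a contradiction to be reconciled. Section 6.3.4.1 does not reset the progression reference at cross-over, while Sections 6.3.4.3, 6.3.5 and 6.3.6 are worded by treatment. On the literal rule, a patient who crossed over with target growth of at least 20% and 5 mm above nadir, and who is only stable on the second drug, is progressive at its first scan.

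In the 100/120 mm example the disputed band is 120 to just under 144 mm. Over the assumed 20% to 50% growth at cross-over, with a nadir of at least 25 mm, the shrinkage needed to leave progression runs from just above 0 to 20.0%. How many patients this would reclassify cannot be computed from the documents.

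The effect is confined to second-drug PFS and to the stable/progressive boundary in second-drug response. First-line PFS and its 80% power stand. The correction is worth making because it is cheap and because the answer should be fixed before second-drug scans are analysed.

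**What to change.** State in Sections 6.3.4.1 and 6.3.6 that, for the analysis of second-drug PFS and response, the CT or MRI required within 4 weeks before cross-over is the baseline for target sums, non-target lesions and new-lesion calls, and that progression is judged against the smallest sum since that drug started. Use the same wording in Sections 6.3.4.3 and 6.3.5. This also supplies the baseline sum for partial response on the second drug, which the plan does not define.

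The cost is one sentence and matching edits. The scan is already collected, and neither sample size nor the primary analysis changes.

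This concerns the analysis reference only. Because Section 3.5.1 makes progression on each arm a reason to end protocol therapy, the sponsor must also reconcile these passages for treatment decisions. No stopping rule is proposed here.

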6.3.4.2 Evaluation of Non-Target Lesions

Complete Response (CR): Disappearance of all non-target lesions and normalization of tumor marker level. All lymph nodes must be non-pathological in size (<10 mm short axis).

Note: If tumor markers are initially above the upper normal limit, they must normalize for a patient to be considered in complete clinical response.

Non-CR/Non-PD: Persistence of one or more non-target lesion(s) and/or maintenance of tumor marker level above the normal limits.

Progressive Disease (PD): Appearance of one or more new lesions and/or unequivocal progression of existing non-target lesions. Unequivocal progression should not normally trump target lesion status. It must be representative of overall disease status change, not a single lesion increase.

Although a clear progression of “non-target” lesions only is exceptional, the opinion of the treating physician should prevail in such circumstances, and the progression status should be confirmed at a later time by the review panel (or Principal Investigator).

6.3.4.3 Evaluation of Best Overall Response

The best overall response is the best response recorded from the start of the treatment until disease progression/recurrence (taking as reference for progressive disease the smallest measurements recorded since the treatment started). The patient's best response assignment will depend on the achievement of both measurement and confirmation criteria.

For Patients with Measurable Disease (i.e., Target Disease)

Target Lesions	Non-Target Lesions	New Lesions	Overall Response	Best Overall Response when Confirmation is Required*
CR	CR	No	CR	≥4 wks. Confirmation**
CR	Non-CR/Non-PD	No	PR	≥4 wks. Confirmation**
CR	Not evaluated	No	PR	
PR	Non-CR/Non-PD/not evaluated	No	PR	
SD	Non-CR/Non-PD/not evaluated	No	SD	Documented at least once ≥4 wks. from baseline**
PD	Any	Yes or No	PD	no prior SD, PR or CR
Any	PD***	Yes or No	PD	
Any	Any	Yes	PD	

* See RECIST 1.1 manuscript for further details on what is evidence of a new lesion.
 
** Only for non-randomized trials with response as primary endpoint.
 
*** In exceptional circumstances, unequivocal progression in non-target lesions may be accepted as disease progression.
 
Note: Patients with a global deterioration of health status requiring discontinuation of treatment without objective evidence of disease progression at that time should be reported as “symptomatic deterioration.” Every effort should be made to document the objective progression even after discontinuation of treatment.
				

For Patients with Non-Measurable Disease (i.e., Non-Target Disease)

Non-Target Lesions	New Lesions	Overall Response
CR	No	CR
Non-CR/non-PD	No	Non-CR/non-PD*
Not all evaluated	No	not evaluated
Unequivocal PD	Yes or No	PD
Any	Yes	PD

* ‘Non-CR/non-PD’ is preferred over ‘stable disease’ for non-target disease since SD is increasingly used as an endpoint for assessment of efficacy in some trials so to assign this category when no lesions can be measured is not advised
		

